## 11.2 Subject demographics and other baseline characteristics

All data for background and demographic variables will be listed by treatment group and subject. Summary statistics will be provided by treatment group.

Relevant medical history, current medical conditions, results of laboratory screens, drug tests and any other relevant information will be listed by treatment group and subject.

## 11.3 Treatments (study drug, rescue medication, other concomitant therapies, compliance)

Data for study drug administration, rescue medication and concomitant therapies will be listed by treatment group and subject.

## 11.4 Analysis of the primary variable(s)

The primary objectives of this study are to preliminarily evaluate the safety, tolerability and efficacy of IV CFZ533 in moderate to severe Myasthenia Gravis patients after 24 weeks of treatment as an add-on therapy to standard of care as compared to placebo.

### 11.4.1 Variable(s)

The safety variables and analysis are detailed in [Section 11.5.2](#).

The primary efficacy variable is the change from baseline in QMG score after 24 weeks of treatment (at week 25 visit). The baseline value will be the predose assessment on Day 1. It is assumed that the change from baseline in QMG score is normally distributed.

### **11.4.3 Handling of missing values/censoring/discontinuations**

No imputation of missing data for dropouts will be done.

Corporate Confidential  
Information

### **11.4.4 Supportive analyses**

In order to assess the robustness of the results, the primary analysis will be repeated on the FAS.

In addition, the changes from baseline in QMG scores at each visit of the treatment period (weeks 5, 9, 13, 17, 21 and 25) will be analyzed using a mixed effect model for repeated measurements. The model may investigate effects for treatment (CFZ533 or placebo), time (visit week), baseline QMG score, treatment by time and baseline by time interactions. An unstructured covariance matrix may be used to model the correlations between the measurements in the same subject. In case of convergence issues, the covariance matrix that best fit the data will be chosen. The estimated treatment differences at each visit will be provided with 90% CI and 2-sided p-values.

Other potentially influent factors such as sex, age at onset of the disease, makers of baseline severity of the disease or prednisone dose may be explored.

## **11.5 Analysis of secondary and exploratory variables**

### **11.5.1 Efficacy / Pharmacodynamics**

The MGC composite is a key secondary endpoint. The changes from baseline in QMG scores at each visit of the treatment period (weeks 5, 9, 13, 17, 21 and 25) will be analyzed using a Bayesian model for repeated measurements. The model may investigate effects for treatment (CFZ533 or placebo), time (visit week), baseline QMG score, treatment by time and baseline by time interactions. An unstructured covariance matrix may be used to model the correlations between the measurements in the same subject. In case of convergence issues, the covariance matrix that best fit the data will be chosen. The estimated treatment differences at each visit will be provided with 90% CI and 2-sided p-values.

Other secondary efficacy variables include:

- proportions of patients requiring rescue therapy (i.e. IV immunoglobulins or plasma exchange)
- mean change from baseline in QMG Score and MGC Score at all visits
- proportion of patients with improvement by  $\geq 3$  points in QMG score
- proportion of patients with worsening by  $\geq 3$  points in QMG score
- proportion of patients intolerant to steroid taper
- proportion of patients who discontinued due to inefficacy or worsening
- Mean change in the Myasthenia Gravis Activities of Daily Living Scales (MG-ADL, MG QOL-15).

The changes from baseline in MG-ADL and MG QOL-15 at each visit until week 25 will be analyzed using the main mixed model as described above for MGC.

The proportions of patients requiring rescue therapy between Week 1 and Week 25 (i.e. IV immunoglobulins or plasma exchange) will be described. Time to first rescue therapy will be described using Kaplan-Meier curves and compared between CFZ533 and placebo using the log-rank test. In case of dropouts, the data will be censored at the last visit before or at Week 25.

The proportion of patients with improvement by  $\geq 3$  points in QMG score at Week 25, the proportion of patients with worsening by  $\geq 3$  points in QMG score at week 25, the proportion of patients intolerant to steroid taper and the proportion of patients who discontinued due to inefficacy or worsening before week 25 will be analyzed via logistic regression with treatment as a factor compared between CFZ533. Additional covariates such as sex, gender, age at onset of MG, QMG score at baseline will be explored. Odds ratios together with 90% CI and p-values will be provided for comparisons of CFZ533 versus placebo utilizing the logistic regression model fitted.

The statistical analysis for exploratory efficacy and PD variables will be described in the RAP.

## 11.5.2 Safety

### Vital signs

All vital signs data will be listed by treatment, subject, and visit/time and if ranges are available abnormalities (and relevant orthostatic changes) will be flagged. Summary statistics will be provided by treatment and visit/time.

### ECG evaluations

All ECG data will be listed by treatment, subject and visit/time, abnormalities will be flagged. Summary statistics will be provided by treatment and visit/time.

### Clinical laboratory evaluations

All laboratory data will be listed by treatment, subject, and visit/time and if normal ranges are available abnormalities will be flagged. Summary statistics will be provided by treatment and visit/time.

### Adverse events

All information obtained on adverse events will be displayed by treatment and subject.

The number and percentage of subjects with adverse events will be tabulated by body system and preferred term with a breakdown by treatment. A subject with multiple adverse events within a body system is only counted once towards the total of this body system.

Corporate Confidential Information

## 11.5.3 Pharmacokinetics

Free CFZ533 plasma concentration data will be listed by treatment, subject, and visit/sampling time point. Descriptive summary statistics will be provided by treatment and visit/sampling time point, including the frequency (n, %) of concentrations below the LLOQ.

Summary statistics will include mean (arithmetic and geometric), SD, CV (arithmetic and geometric), median, minimum and maximum. An exception to this is Tmax where median, minimum and maximum will be presented. Concentrations below LLOQ will be treated as zero in summary statistics and will not be considered for PK parameter calculations. A geometric mean will not be reported if the dataset includes zero values. PK parameters will be calculated as described in [Section 8.5](#) and will be listed by treatment and subject.

Population modeling of PK data using compartmental, non-linear or mechanistic approaches (i.e. together with PD endpoints), may be performed as appropriate, and will be reported in a separate, standalone modeling and simulation report. During modeling activities, the broad principles outlined in the FDA Guidance for Industry: Population PK, will be followed.

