### Pharmacokinetic definitions and symbols

AUC tau	The area under the plasma concentration-time curve from time zero to the end of the dosing interval tau [ $\mu\text{g} \times \text{day} / \text{mL}$ ]
AUC tau,ss	The area under the plasma concentration-time curve from time zero to the end of the dosing interval tau, at steady state [ $\mu\text{g} \times \text{day} / \text{mL}$ ]
C av,ss	The average steady state plasma concentration during multiple dosing [ $\mu\text{g} / \text{mL}$ ]
C max	The observed maximum plasma concentration following drug administration [ $\mu\text{g} / \text{mL}$ ]
C max,ss	The observed maximum plasma concentration following drug administration at steady state [ $\mu\text{g} / \text{mL}$ ]
C min,ss	The lowest plasma concentration observed during a dosing interval at steady state [ $\mu\text{g} / \text{mL}$ ]
T max	The time to reach the maximum concentration after drug administration [day]

Corporate Confidential Information

Corporate Confidential Information

Corporate Confidential Information

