## 8.5 Pharmacokinetics

PK blood samples will be collected from all patients, at baseline and during the treatment and follow-up periods at the timepoints defined in the Assessment Schedule (Table 8-1).

Untreated samples (placebo-treated patients) will not be analyzed unless a safety issue suggests otherwise or there is clinical suspicion of treatment group misclassification.

Corporate Confidential Information

For standard PK abbreviations and definitions see the list provided at the beginning of this protocol.

The following PK parameters will be determined using the actual recorded sampling times and non-compartmental method(s) with Phoenix WinNonlin (Version 6.2 or higher):  $C_{max}$ ,  $C_{max,ss}$ ,  $C_{min,ss}$ ,  $T_{max}$ ,  $AUC_{tau}$ ,  $AUC_{tau,ss}$  and  $C_{av,ss}$  from the plasma concentration-time data.

The linear trapezoidal rule will be used for AUC calculation.

A SOM accompanies this protocol, providing operational details for study conduct (incl. subject numbering, blood log with sample numbers). Further details on sample collection, processing and shipment will be provided in the Central Lab Manual. The detailed methods of analysis and data will be provided in the Bioanalytical Data Report.

Corporate Confidential Information

Corporate Confidential Information

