6.1.5 Graphical presentation of results

Arithmetic mean (SD) and geometric mean (95% CI) plasma concentration data will be plotted across time.

Overlaying individual plasma concentration-time profiles will be generated.

Corporate Confidential Information

7 Statistical methods for Pharmacodynamic (PD) parameters

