8.1.3 Graphical presentation of results

Boxplots to visualize trends in longitudinal safety data (vitals, ECG, lab parameter) will be created.

9 Statistical methods for Biomarker data

All biomarker data (except for hypothesis-free platforms) will be listed by treatment, subject, and visit/time. Summary statistics for each variable (absolute and change from baseline) will be provided by treatment and visit/time.

In the summary tables, the frequency (n, %) of values below the LLOQ and above the ULOQ, respectively, will be included.

In case of censored values (values below the LLOQ and/or values above the ULOQ), the summary statistics (arithmetic mean, SD, geometric mean and CV% of geometric mean) will be calculated as the maximum likelihood estimates using a parametric model for data that can be right censored and left censored assuming the data being normally or log-normally distributed.

Corporate Confidential Information

Concomitant immunosuppressive therapies trough levels

Plasma/blood concentrations for mycophenolic acid (MPA), azathioprine metabolite(s) or cyclosporine will be listed by treatment, subject, and visit/sampling time point. No descriptive summary statistics will be provided.

Corporate Confidential Information

10 Reference list

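### Omitting concentrations below LLOQ from PK parameters biases Cmin,ss upward whenever a steady-state trough is below LLOQ, and the zero rule can leave gaps in the planned geometric mean plot

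*Protocol*

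**What the plan says.** Protocol 11.5.3 gives one sentence with two rules: "Concentrations below LLOQ will be treated as zero in summary statistics and will not be considered for PK parameter calculations". The sentence after it adds: "A geometric mean will not be reported if the dataset includes zero values".

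The PK definitions at the front of the protocol describe Cmin,ss as "The lowest plasma concentration observed during a dosing interval at steady state". Protocol 8.5 derives the parameters "using the actual recorded sampling times and non-compartmental method(s) with Phoenix WinNonlin".

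For concentrations by treatment and time point, Protocol 11.5.3 promises: "Summary statistics will include mean (arithmetic and geometric), SD, CV (arithmetic and geometric), median, minimum and maximum". It also asks for a listing of every concentration and for summaries "including the frequency (n, %) of concentrations below the LLOQ".

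SAP 6.1.5 plans this plot: "Arithmetic mean (SD) and geometric mean (95% CI) plasma concentration data will be plotted across time". It plans overlaid individual profiles as well. The readable SAP text gives no rule for time points that contain zeros. SAP 6.1.2 is not in the public text.

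For biomarkers, SAP section 9 takes a different route: with values beyond the quantification limits, the summary statistics, including the geometric mean, are "calculated as the maximum likelihood estimates using a parametric model for data that can be right censored and left censored".

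**The concern.** A sample below LLOQ is informative: the concentration is known to lie between zero and LLOQ. The plan uses that information in one output and discards it in another. In the concentration table the sample counts as zero. In the parameter that is meant to describe the lowest exposure, it does not exist. The samples lost to Cmin,ss are exactly the ones that define it, and they come from the patients with the lowest exposure.

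The second problem is a mismatch between the two documents. The protocol withholds the geometric mean once a zero is present, and the SAP plots it over the whole time course. Follow-up is where zeros are most likely. It is also the period covered by the secondary objective on decay of efficacy, and it bears on the objective on duration of target engagement (Protocol 2.2).

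At stake is the description of trough exposure and washout in a study with PK and immunogenicity among its secondary objectives. The QMG analysis does not use these values.

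**Working it through.** The documents give no LLOQ, trough or half-life, so there is no PK figure of the plan's own to reproduce.

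**1. Direction of the error in Cmin,ss.** Let L be the LLOQ, and let a patient have a steady-state sample below L.

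- The patient's true minimum is below L.
- The parameter may use only values at or above L.
- If such a value remains in the interval, the reported Cmin,ss is at least L, so it exceeds the true minimum.
- If none remains, Cmin,ss is missing. Every Cmin,ss still in the summary is at least L, so only patients below all of these have been removed. The arithmetic and geometric means rise; the median rises or stays.
- If no steady-state sample is below L, nothing changes.

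The error, when it occurs, therefore goes one way only.

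**2. Illustrative size.** All inputs here are assumptions: 18 patients; sustained troughs log-normal with geometric mean 30 and CV 50%; LLOQ 0.1, 0.5 or 1.0 in the same units; k patients with a true trough between 0.02 and 1 times LLOQ; next quantifiable sample 1 to 50 times LLOQ; 4,000 simulated trials. For LLOQ 0.5 and k = 2:

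| Handling | Geometric mean Cmin,ss | Arithmetic mean Cmin,ss |
|---|---|---|
| True values | 17.4 | 29.9 |
| Plan's rule, next quantifiable sample used | 23.9 | 30.6 |
| Plan's rule, patients missing | 30.3 | 33.6 |
| Values below LLOQ set to zero | not defined | 29.9 |

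The geometric mean is inflated 23.9/17.4 = 1.37 times or 30.3/17.4 = 1.74 times. Over k = 1 to 4 and the three LLOQ values, the range is 27.9/23.8 = 1.2 to 13.2/7.0 = 1.9 if the next sample is used, and 30.2/23.8 = 1.3 to 30.3/7.0 = 4.3 if the patients become missing. The arithmetic mean moves by about 0 to 10% and 6 to 28%. These figures show only that the effect can matter. They do not estimate what will happen in this trial.

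**3. Loss of the geometric mean.** I read the dataset in the protocol's sentence as the values at one time point, because that is the level of the summaries. Placebo samples are normally not analysed (Protocol 8.5), so the relevant number is the CFZ533 arm: 18 evaluable or 22 randomized (Protocol 11.6). If each patient independently has probability p of being below LLOQ, the chance that the geometric mean is withheld is 1 − (1 − p)^n.

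| Assumed p | n = 18 | n = 22 |
|---|---|---|
| 1% | 16.5% | 19.8% |
| 2% | 30.5% | 35.9% |
| 5% | 60.3% | 67.6% |
| 10% | 85.0% | 90.2% |
| 20% | 98.2% | 99.3% |

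For example, at p = 5% and n = 18: 1 − 0.95^18 = 0.603.

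**4. Are values below LLOQ foreseeable?** PK is sampled at baseline, on treatment and in follow-up (Protocol 8.5). The last dose is at Week 21, the treatment period runs 4 weeks beyond it, and follow-up lasts another 24 weeks (Protocol 3.1), so the study ends about 4 + 24 = 28 weeks after the last dose. Patients who stop dosing after rescue therapy may stay for follow-up (Protocol 6.9). The plan itself asks for the frequency below LLOQ. Values below LLOQ are to be expected in follow-up. Whether any arises at a steady-state trough is not known.

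**The case against.** The strongest reply is that lost exposure remains in plain sight. A patient with a trough below LLOQ appears in the n (%) below LLOQ, the minimum, the listing and the individual profiles. A reader might infer that the plan conceals loss of exposure; those outputs rule that out. What stands on the other side is narrower: the frequency below LLOQ is promised for concentrations, and no readable text flags a Cmin,ss that was derived after a trough had been dropped.

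Second, the Cmin,ss effect is conditional. Nothing readable shows that any steady-state trough under this regimen would be below LLOQ. This is correct, and it limits the point to what the rule does when the case arises.

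Third, setting values to zero hardly moves an arithmetic mean. The shift is less than LLOQ times the fraction of patients below it, and the illustration gives 29.9 either way. This stands; the arithmetic mean is not part of the problem.

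Fourth, only the affected time points lose the geometric mean, and the arithmetic mean and individual profiles are still plotted. In late washout, with most values below LLOQ, no method gives a useful geometric mean. This also stands, and the fix allows for it.

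Fifth, a rule may exist in SAP 6.1.2 or in the redacted part of Protocol 8.5. That cannot be checked. If there is one, it should be reconciled with Protocol 11.5.3.

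**Conclusion.** The point holds in a limited form. Protocol 11.5.3 treats the same sample in two incompatible ways. When a steady-state trough is below LLOQ, the group Cmin,ss is biased upward, whether the patient's value is overstated or missing. The direction follows from the definition alone. The frequency and size cannot be derived from the documents.

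The geometric mean rule and the SAP 6.1.5 plot do not fit together. One value below LLOQ is enough to leave a gap, with a chance of about 30% to 90% per time point for assumed rates of 2% to 10% and 18 to 22 patients.

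The documents do not support three stronger readings. One is that Cmin,ss will in fact be overstated by some known factor; that needs a half-life and sampling times that are not readable. Another is that the geometric mean of Cmin,ss itself disappears; values below LLOQ never enter that parameter as zeros, so only concentration summaries are affected. The third is that conclusions on efficacy are at risk: PK is a secondary objective, target engagement is measured directly through CD40, and the QMG analysis does not use these values.

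The correction is still worth making, because it removes a one-directional bias at little cost.

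**What to change.** In Protocol 11.5.3 and SAP section 6, reconciled with any rule in SAP 6.1.2:

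- **Cmin,ss.** When the steady-state trough is below LLOQ, report that patient's Cmin,ss as below LLOQ. Do not replace it by the next quantifiable sample or leave it missing. Summarise Cmin,ss by median, range and n (%) below LLOQ.
- **Geometric mean plot.** State what is shown at time points with values below LLOQ. One option is the censored maximum-likelihood estimate that SAP section 9 specifies for biomarkers when most values are quantifiable, and otherwise the median with n (%) below LLOQ.

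The cost is a small edit to both documents before database lock and some programming; the documents do not show that the biomarker method is already programmed. The censored estimate also brings a distributional assumption in about 18 to 22 patients, which a subgroup that loses exposure would strain. The Cmin,ss change needs no such assumption.

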## 11.6 Sample size calculation

The sample size is based on the primary efficacy endpoint and the primary analysis described in [Section 11.4.2](#)

Corporate Confidential Information

A sample size of 36 evaluable patients (18 on CFZ533, 18 on placebo) was determined, assuming a SD of 5.5 ([Zinman et al 2007](#)) for the QMG endpoint. To account for approximately 20% anticipated dropouts, 44 patients will be randomized in this study (22 on CFZ533 and 22 on placebo).

To account for potential discontinuations due to non-detectable AChR or MuSK autoantibodies, the sample size might be increased to compensate the discontinued seronegative patients. The operating characteristics of this design are shown on [Figure 11-1](#) below. The probability of reaching the target efficacy (success) at final analysis is about 8% if CFZ533 is equal to placebo, and it is >80% if the true difference between CFZ533 and

placebo is  $\geq 4.5$ . At the planned IA the probability of success is 42% if the true difference between CFZ533 and placebo is  $\geq 4.5$  and the probability of stopping for futility is 5% if CFZ533 is equal to placebo. This sample size was considered adequate to preliminarily evaluate the efficacy of CFZ533 in the treatment of myasthenia gravis.

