### 3.6 Risks and benefits

It is not known if there could be a benefit to patients from treatment with CFZ533.  
Corporate Confidential Information

Corporate Confidential Information

The risk to subjects in this trial will be minimized by adherence to the inclusion/exclusion criteria, close clinical monitoring, and targeted monitoring/follow-up visit safety assessments.

Corporate Confidential Information

Hypersensitivity or infusion reactions can manifest with itching, flushing, headache, nausea/vomiting, hypotension, urticaria, bronchospasm, or angioedema. No such events were found in the Phase 1 study with CFZ533. In this study, CFZ533 will be administered as a 2-hour infusion where such hypersensitivity reactions can still occur. Subjects will be monitored up to 4 hours after the end of the infusion at each visit.

Subjects treated with CFZ533 may be at an increased risk of infection.  
Corporate Confidential Information

Administration of CFZ533 is expected to result in immunosuppression, with a decreased capacity to mount a response to novel immunogens requiring T cell-dependent B cell activation (potentially including bacterial, viral, fungal and parasitic origin) when full receptor occupancy has been achieved.

Corporate Confidential Information

In addition, subjects will have adequate preformed antibody to maintain protective humoral response for extended periods of time (months). Subjects enrolled in this study will be carefully monitored for signs and symptoms of an infection.

Corporate Confidential Information

Although not expected in this clinical study, the investigator will monitor for signs, symptoms and laboratory results consistent with clinically significant inflammation as well as for changes in renal function and signs of acute kidney injury as per local practice.

There has been no evidence that CFZ533 has an effect on clinical coagulation parameters, and no evidence from preclinical or clinical studies that CFZ533 presents an increased risk of thromboembolic events (TE).

Corporate Confidential Information

Nevertheless, standard coagulation parameters and TEs will be carefully monitored throughout the study.

The overall risk-benefit supports further investigation in patients with autoimmune diseases such as MG patients. However, there may be unknown risks of CFZ533 which may be serious and unforeseen.

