All blinded safety data, including disease specific events, will be evaluated by the Sponsor and Investigator on an ongoing basis and at scheduled meetings. The study may be put on hold pending further data analysis, if the principal investigator or the Sponsor considers that the number and/or severity of AEs justify discontinuation of the study.

In addition, a DMC will be instituted (see [Section 10.3](#)) with the aim to review safety data regularly (and efficacy data, if required) as outlined in their charter and at ad hoc meetings. The DMC can recommend stopping the entire trial if it is considered unsafe or unethical to continue administering CFZ533.

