## 7.5 Early study termination

The study can be terminated at any time for any reason by Novartis. Should this be necessary, subjects should be seen as soon as possible and treated as a prematurely withdrawn subject and complete their EoS visit assessments as per Assessment Schedule ([Table 8-1](#)). The investigator may be informed of additional procedures to be followed in order to ensure that adequate consideration is given to the protection of the subject's interests.

The investigator will be responsible for informing IRBs/IECs of the early termination of the trial.

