**Figure 11-1 Operating characteristics for the planned interim and final analyses**

[figure not shown]

Figure 11-1 shows the operating characteristics curves for the planned interim and final analyses. The horizontal axis shows the difference CFZ533 minus placebo in mean QMG change from baseline (from 0 to 6). The vertical axis displays the probabilities (i) success (target efficacy, green curves), (ii) futility (red curves), and (iii) indeterminate (neither success nor futility achieved (yellow curves)).

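### Is the interim futility look too lenient if it stops only 5% of trials of an inert drug?

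*Protocol*

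**What the plan says.** Section 11.6 sets the final size: "A sample size of 36 evaluable patients (18 on CFZ533, 18 on placebo) was determined, assuming a SD of 5.5", with 44 randomized to allow for about 20% dropout. It gives the chance of final success as about 8% if there is no difference and above 80% if the true difference is at least 4.5.

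For the interim it gives two figures. On success: "At the planned IA the probability of success is 42% if the true difference between CFZ533 and placebo is" at least 4.5. On futility: "the probability of stopping for futility is 5% if CFZ533 is equal to placebo".

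Figure 11-1 is described as showing success, futility and indeterminate curves for both analyses: "The horizontal axis shows the difference CFZ533 minus placebo in mean QMG change from baseline (from 0 to 6"). The figure is not in the public text.

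The synopsis states the target efficacy: at least 90% probability that the difference is 0 or more, and 50% probability that it is 3 or more. A positive difference favours CFZ533.

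The interim size, interim rules and prior are not visible. Section 11.6 relies on Section 11.4.2, which is in the contents but withheld, and a confidentiality mark precedes the sample size paragraph. The SAP passes from Section 3 to Section 5 over another such mark. These are redactions, not omissions from the plan.

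**The concern.** A futility look is usually there to end a trial of a drug that does not work. One that lets 95% of such trials continue seems to do little of that job. Section 3.6 warns: "Subjects treated with CFZ533 may be at an increased risk of infection". Patients in an inert-drug trial would carry that risk without benefit.

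A second suspicion is that the 5% is mislabelled. A small stopping probability is the figure one expects to see quoted under a worthwhile effect, as the price of the look, rather than under no effect, where a high value is wanted. If so, readers of Section 11.6 would be misinformed about the interim rule.

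**Working it through.** **Inputs.** From the protocol: SD 5.5; 18 per arm at the final analysis; 1:1 allocation; the 90%/50% target; printed probabilities of about 8%, above 80%, 42% and 5%. Assumed, because redacted: a flat prior, a futility rule on the observed difference, and n evaluable patients per arm at the interim. SE(n) = 5.5 × √(2/n).

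**Step 1: the plan's own final figures.** SE(18) = 1.833. The 90% condition needs an observed difference of 1.2816 × 1.833 = 2.35. The 50% condition needs 3, so it binds.

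- Success at no effect: 1 − Φ(3/1.833) = 5.1%, against about 8% printed.
- Success at 4.5: Φ(1.5/1.833) = 79.3%, against above 80% printed.

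This single-look reading misses both, so something withheld matters. Two repairs work:

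- Count interim success, with its cut-off at 4.5 + 0.202 × SE(n) to give the printed 42%. Combined success at 0 and 4.5 is then 12.1% and 82.9% (4 per arm), 8.8% and 81.9% (6), 7.8% and 81.4% (7), 6.4% and 80.6% (9), 5.4% and 79.8% (12). The best fit is 6 to 7 per arm.
- Let the prior move the final cut-off to 1.405 × 1.833 = 2.58. A single look then gives 8.0% and Φ(1.92/1.833) = 85.3%. This fits both figures and says nothing about the interim size.

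A third clue points elsewhere. If the 90%/50% target also applied at the interim, success at 4.5 would be 39% (3 per arm), 45% (4) or 55% (6), so the printed 42% would suggest 3 to 4 per arm. The interim size cannot be recovered from the public text.

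**Step 2: what the printed 5% implies.** The boundary is f = −1.645 × SE(n). Success lost is P(interim < f and final ≥ c) at a true 4.5, from a bivariate normal with correlation √(n/18).

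**Step 3: a stricter boundary.** Choose f so that the loss at 4.5 is 1 percentage point, then read P(stop) at no effect.

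| n per arm | SE(n) | f for 5% stop | points lost at 4.5 (c = 3) | P(stop) at no effect, 1-point loss, c = 3 | same, c = 2.58 |
|---|---|---|---|---|---|
| 3 | 4.49 | −7.39 | 0.14 | 16% | 14% |
| 4 | 3.89 | −6.40 | 0.06 | 22% | 19% |
| 6 | 3.18 | −5.22 | 0.010 | 34% | 31% |
| 7 | 2.94 | −4.84 | 0.004 | 41% | 37% |
| 9 | 2.59 | −4.26 | <0.001 | 54% | 49% |
| 12 | 2.25 | −3.69 | <0.001 | 71% | 66% |

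**Step 4: the price (c = 3).** At 6 and 7 per arm the 1-point boundary stops 8.9% and 10.5% of trials at a true difference of 3, and 3.4% and 3.9% at 4.5. Most of those at 4.5 (71% and 74%) would have failed anyway. At 9 per arm, combined success at 4.5 falls from 80.6% to 79.6%, below the stated 80%. With 6 to 7 per arm in the interim, at most 44 − 12 = 32 or 44 − 14 = 30 patients lie outside it. With a Week 25 endpoint and no stated enrolment pace, the number actually spared is unknown.

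**Step 5: could the 5% be mislabelled?** At 6 and 7 per arm, a 5% stop at a true 4.5 would mean 41.0% and 45.5% at no effect; a 5% stop at a true 3 would mean 24.2% and 26.6%. A different event also fits: interim success at no effect is 5.3% at 6 per arm and 4.2% at 7. The visible text cannot choose between these and the sentence as printed.

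**The case for a change.** The strongest case for a change is that the direction does not depend on the assumptions. At every interim size tried, the printed boundary costs almost nothing at 4.5, and a 1-point cost would stop well over 5% of inert-drug trials. No patients would be added, and only the sponsor's existing calculation would need rerunning. The other brakes are no substitute. Section 7.4 says "The DMC can recommend stopping the entire trial if it is considered unsafe or unethical to continue administering CFZ533" and Section 7.5 says "The study can be terminated at any time for any reason by Novartis", but the visible triggers are about safety or are discretionary; none is an efficacy threshold.

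The direction stands. The rest is weaker. The missing rationale may be in the withheld text, so its absence proves nothing. The gain ranges fivefold with an interim size nobody outside can know, and the Bayesian repeated-measures model could give interim precision other than 5.5 × √(2/n). One point of success at 4.5 is a threshold brought from outside the plan. Each extra stop also gives up safety, PK/PD and immunogenicity data, and possibly an indeterminate result that could still inform development.

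**Conclusion.** No change follows. The printed 5% describes a very lenient futility look, but nothing in the documents shows it to be an error. In a non-confirmatory Phase IIa study that lists safety and tolerability first among its primary objectives, declining to stop on perhaps a dozen patients unless the drug looks clearly worse than placebo is a defensible choice.

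A stricter rule would buy a 14% to 71% chance of stopping an inert-drug trial, for interims of 3 to 12 per arm, with SD 5.5, a flat-prior-type rule and a final cut-off of 2.58 to 3. The price is 1 point of success at 4.5, about 9% to 10% of trials stopped at a true difference of 3 (6 to 7 per arm, cut-off 3), and the data those trials would have produced. Reasonable statisticians would differ on that exchange, and its benefit in patients cannot be computed.

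Whether the 5% carries the right label is a question for whoever holds the curves behind Figure 11-1. Reading the futility curve at zero settles it. If the event or the true difference were mislabelled, that would be a clerical slip in one sentence and the design would be unaffected.
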